12.2. Safety Analysis

The safety analysis will be performed in all treated subjects. AE data will be listed individually and incidence of AEs summarized by system organ class and preferred terms within a system organ class for each cohort. When calculating the incidence of AEs, each AE (based on preferred terminology defined by CTCAE version 5.0) will be counted only once for a given subject. In analyses of grade and causality, if the same AE occurs on multiple occasions, the highest grade and strongest relationship to study drug will be assumed. If 2 or more AEs are reported as a unit, the individual terms will be reported as separate experiences.

Changes in vital signs, hematology and clinical chemistry parameters from baseline to the end of the study will be examined. Toxicity will be tabulated by type and grade. Toxicities will be characterized according to the CTCAE version 5.0. Treatment-emergent changes from normal to abnormal values in key laboratory parameters will be identified.

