6.2. Relationship

The relationship of an AE to the administration of the study drug is to be assessed by the investigator according to the following definitions:

- No (unrelated, not related, no relation): The time course between the administration of study drug and the occurrence or worsening of the adverse event rules out a causal relationship and another cause (concomitant drugs, therapies, complications, etc.) is suspected.
- Yes (related): The time course between the administration of study drug and the occurrence or worsening of the adverse event is consistent with a causal relationship and no other cause (concomitant drugs, therapies, complications, etc.) can be identified.

The following factors should also be considered:

- The temporal sequence from study drug administration The event should occur after the study drug is given. The length of time from study drug exposure to event should be evaluated in the clinical context of the event.
- Underlying, concomitant, intercurrent diseases Each report should be evaluated in the context of the natural history and course of the disease being treated and any other disease the subject may have.
- Concomitant medication The other medications the subject is taking or the treatment the subject receives should be examined to determine whether any of them might be recognized to cause the event in question.
- Known response pattern for this class of study drug Clinical and/or preclinical data may indicate whether a particular response is likely to be a class effect.
- Exposure to physical and/or mental stresses The exposure to stress might induce adverse changes in the recipient and provide a logical and better explanation for the event.
- The pharmacology and pharmacokinetics of the study drug The known pharmacologic properties (absorption, distribution, metabolism, and excretion) of the study drug should be considered.

Assessment of Grade:

The investigator will make an assessment of grade for each AE and SAE reported during the study, which will be recorded in the CRF. The assessment will be based on the National Cancer Institute's CTCAE (Version 5.0) and graded as shown below:

- Grade 1: Mild; asymptomatic or mild symptoms; clinical or diagnostic observations only; intervention not indicated
- Grade 2: Moderate; minimal, local or noninvasive intervention indicated; limiting ageappropriate instrumental activities of daily living

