- Grade 3: Severe or medically significant but not immediately life-threatening; hospitalization or prolongation of hospitalization indicated; disabling; limiting self-care activities of daily living
- Grade 4: Life-threatening consequences; urgent intervention indicated
- Grade 5: Death related to AE

Any AE that changes in grade during its course will be recorded in the CRF at the highest level experience by the subject.

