10.2. Secondary Endpoint

The secondary endpoint is as follows:

Safety assessed by the following measures:

- Number of patients who have grade 3 or higher drug-related toxicities
- Frequency of drug-related toxicity by grade
- Nivolumab- and relatlimab-related infusion reactions
- Immune-related AEs
- Unacceptable toxicities
- Vital signs: BP, pulse, respiratory rate, temperature
- Physical examination
- Changes in ECG readings
- Clinical hematology: complete blood count (CBC) with differential ANC, ALC, AEC, and platelet count
- Clinical serum chemistry: sodium, potassium, chloride, bicarbonate, glucose, BUN, creatinine, LDH, ALT, AST, alkaline phosphatase, total bilirubin, direct bilirubin, amylase, lipase, total protein, albumin, calcium, magnesium, and phosphorus
- TSH, T3, Free T4
- Cardiac troponin

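### For a recurring adverse event, Section 12.2 takes the highest grade and the strongest relationship without tying them to one occurrence, so the grade 3+ drug-related count can be overstated

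*Combined protocol and SAP*

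**What the plan says.** Section 12.2 (Safety Analysis) counts adverse events by subject and preferred term: each term "will be counted only once for a given subject". The rule for recurrences opens with "In analyses of grade and causality" and continues that "if the same AE occurs on multiple occasions, the highest grade and strongest relationship to study drug will be assumed". The same section also promises individual listings of adverse events and a tabulation of toxicity by type and grade.

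Section 10.2 has one secondary endpoint, safety, assessed by a list of measures. The first two are "Number of patients who have grade 3 or higher drug-related toxicities" and "Frequency of drug-related toxicity by grade". Neither comes with a derivation rule of its own.

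Section 6.2 works at the level of the single event. On causality: "The relationship of an AE to the administration of the study drug is to be assessed by the investigator according to the following definitions". The scale has two levels, No and Yes. On severity: "The investigator will make an assessment of grade for each AE and SAE reported during the study, which will be recorded in the CRF". A separate rule covers one continuing event: "Any AE that changes in grade during its course will be recorded in the CRF at the highest level experience by the subject".

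**The concern.** Grade and relationship are two attributes of one occurrence. Section 12.2 takes the maximum of each over all occurrences of a term and does not link the two. With a two-level relationship scale, a single related occurrence is enough to label the whole subject-term record as related, at whatever grade the worst occurrence reached. The first two measures in Section 10.2 are joint statements about grade and relatedness, so they are where the missing link matters.

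Two summaries are at stake: the number of patients with severe drug-related toxicity, and the grade distribution of drug-related toxicity. Safety is the trial's only secondary endpoint, and with at most 32 evaluable patients per cohort one misclassified patient is visible in the percentage.

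**Working it through.** The plan states no figure that bears on this point, so there is nothing to reproduce first. The check compares two derivations.

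**Definitions.** For one subject and one preferred term, each occurrence has a grade from 1 to 5 and a relationship of No or Yes.
- Rule in Section 12.2, applied jointly: flag if the maximum grade over all occurrences is at least 3 and the strongest relationship is Yes.
- Occurrence-level rule: flag if at least one single occurrence is both grade 3 or higher and related.

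**Worked case.** A related grade 2 AST rise leads to a dose hold, and later an unrelated grade 3 AST rise occurs. Both are reportable under Section 6.1.1: the first because study drug was interrupted (Section 5.2 holds drug for a related rise to at least grade 2), the second as a grade 3 result that has worsened from baseline. The Section 12.2 rule gives max(2, 3) = 3 and max(Yes, No) = Yes, so the subject is counted as grade 3 related. The highest grade among related occurrences is 2, so the occurrence-level rule does not count the subject.

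**Direction.** There are 5 × 2 = 10 possible occurrences: 3 grade 3+ unrelated, 2 low-grade related, 2 low-grade unrelated and 3 grade 3+ related. The rules disagree when there is no grade 3+ related occurrence but at least one grade 3+ unrelated and at least one low-grade related occurrence.
- One occurrence: 0 of 10 disagree.
- Two occurrences: 3 × 2 × 2 orders = 12 of 10² = 100.
- Three occurrences: 7³ − 4³ − 5³ + 2³ = 343 − 64 − 125 + 8 = 162 of 10³ = 1,000.

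Every disagreement is an over-count. An under-count is impossible, because one grade 3+ related occurrence satisfies both maxima. These are shares of possible combinations, not expected frequencies.

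**Grade distribution.** For the second measure, any shift of grade matters, not only one across the grade 3 line. With two occurrences, the drug-related grade is overstated when exactly one is related and the unrelated one has the higher grade: 10 ordered grade pairs × 2 orders = 20 of 100.

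**Size.** The share d of subjects affected is not in the documents. It is an assumption, shown from 0% to 10%. Here, affected means a discordant recurrence and no genuine grade 3+ related event of any term.
- Effect of one such subject: 1/32 = 3.1 percentage points in a full cohort, and 1/18 = 5.6 in a cohort stopped after stage 1.
- Expected excess in 32 subjects is 32 × d; the chance of at least one is 1 − (1 − d)³².

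| Assumed d | Expected excess per 32 | Chance of at least one in 32 |
|---|---|---|
| 0% | 0 | 0% |
| 1% | 0.3 | 27.5% |
| 2% | 0.6 | 47.6% |
| 5% | 1.6 | 80.6% |
| 10% | 3.2 | 96.6% |

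**The case against.** The case for leaving the text alone has four parts.

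1. **Section 12.2 does not say that grade and causality are cross-tabulated.** The only grade table it names is by type and grade, without causality. If the two attributes are summarised separately, each maximum is a legitimate worst-case summary. This stands, and it is why the point is conditional. It does not settle the matter: the two measures in Section 10.2 are joint, and the plan offers no other rule for them.

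2. **Discordant recurrences are narrowed by other rules.** Section 6.1.1 makes a grade 1 or 2 laboratory abnormality an adverse event only if it is clinically significant, is serious, or leads to interruption or discontinuation of study drug. It also excludes expected progression of the disease. Section 6.2 records a continuing event once, at its highest grade, and sets a demanding standard for calling an event unrelated. All of this stands. A routine grade 1 AST rise would usually not enter the data at all. The path is not closed, as the worked case shows.

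3. **The convention is conservative.** It cannot hide a true severe related event, and the individual listings keep each occurrence visible. This stands. The summary count could still be too high.

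4. **No decision uses the count.** The conclusion on activity rests on the response rate, and the halting rule in Section 4.7 uses separately defined first-cycle toxicities. This stands, and it limits the consequence to reporting.

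A reader might go further and infer that the plan certainly counts toxicities that never occurred, that it inflates the severe drug-related rate by a material amount, or that the inflation grows with follow-up. The documents support none of these. They do not say that the collapsed record feeds the Section 10.2 measures, they give no recurrence or discordance frequencies, and cumulative incidence generally rises with follow-up under either derivation.

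**Conclusion.** The point holds as a conditional one. If the recurrence rule in Section 12.2 is applied to the two joint measures in Section 10.2, it can classify a subject as having a grade 3 or higher drug-related toxicity that no single occurrence showed. For this to change the patient count, four things must coincide: the same preferred term at least twice in one subject, every grade 3+ occurrence of it judged unrelated, a lower-grade occurrence judged related, and no genuine grade 3+ related event of another term. The error goes upward only.

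The size is unknown. The figure of 0 to 3.2 subjects per 32 rests wholly on the assumed range of 0% to 10%, and zero is a possible answer. It also takes 32 as the denominator. The safety population is all treated subjects, which could be somewhat larger where Section 10.1 allows a treated subject to be replaced. The issue concerns how the secondary endpoint is reported; it touches neither the primary analysis nor the halting rule.

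**What to change.** In Section 12.2, replace the recurrence rule with: *For all-causality summaries, use the highest grade over all occurrences; for drug-related summaries, use the highest grade among occurrences assessed as related.*

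No new data are needed, because Section 6.2 already assesses grade and relationship for each event. No true severe related event is lost, since a related grade 3+ occurrence is itself among those over which the maximum is taken. The cost is a minor change in table programming. The drug-related grade counts would also no longer follow the worst-case convention, so anyone comparing them with a study that keeps that convention should be told of the difference.

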3. PATIENT SELECTION

3.1. Eligibility Criteria

- 3.1.1. Age ≥ 18 years.
- 3.1.2. ECOG performance status of 0-1 (Appendix A).
- 3.1.3. Patients with histologically proven metastatic or locally advanced microsatellite stable (MSS) colorectal adenocarcinoma.
- 3.1.4. Cohort A: Primary lesion has a composite PD-L1/Mucin (CPM) score $\geq 15\%$.
- 3.1.5. Cohort B: Primary lesion has a composite PD-L1/Mucin (CPM) score < 15%.
- 3.1.6. Cohort C: Prior surgical resection of primary tumor. Prospective biomarker evaluation not required.
- 3.1.7. Patients who have received at least one prior cancer chemotherapy regimen in the locally advanced/metastatic setting. Adjuvant therapy can only be counted if recurrence occurred within 6 months of completing systemic chemotherapy.

- Radiosensitizing doses of chemotherapy are not considered systemic chemotherapy. Patients should be considered for standard therapies.
- 3.1.8. Presence of at least one lesion with measurable disease as defined by 10 mm in longest diameter for a soft tissue lesions or 15 mm in short axis for a lymph node by RECIST 1.1.
- 3.1.9. Patients must have available archival tissue from the surgical resection of their primary tumor for CPM score determination.
- 3.1.10. Patient's acceptance to have a tumor biopsy of an accessible lesion at baseline and on treatment if the lesion can be biopsied with acceptable clinical risk (as judged by the investigator).
- 3.1.11. Life expectancy of greater than 3 months.
- 3.1.12. Patients must have normal organ and marrow function as defined below:

 $\begin{array}{lll} \text{-} & \text{Leukocytes} & & \geq 2,000/\text{mm}^3 \\ \text{-} & \text{Absolute neutrophil count} & & \geq 1,500/\text{mm}^3 \\ \text{-} & \text{Platelets} & & \geq 100,000/\text{mm}^3 \\ \text{-} & \text{Hemoglobin} & & \geq 8.5 \text{ g/dL} \end{array}$

- Total bilirubin $\leq 1.5 \text{ x ULN}$ except subjects with Gilbert's

Syndrome, who must have normal direct

bilirubin

- AST(SGOT) and ALT(SGPT) $\leq 3.0 \text{ x ULN}$ - Albumin $\geq 2.8 \text{ g/dl}$

- Lipase and amylase < 1.5 x ULN Subjects with values > 1.5

ULN may enroll if there are neither clinical nor radiographic signs of a pancreatitis.

- Creatinine $\leq 1.5 \text{ x ULN or creatinine clearance (CrCl)}$

≥ 40 mL/min (if using the Cockroft-Gault

formula below):

Female CrC1 = (140 - age in years) x weight in kg x 0.8572 x serum creatinine in mg/dL

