5.2. Dose Delays

In some cases, the natural history of select AEs associated with immunotherapy can differ from and be more severe than AEs caused by other therapeutic classes. Early recognition and management may mitigate severe toxicity.

Guidance for Investigators is provided in the current relatlimab and nivolumab Investigator's Brochures. Additionally, management algorithms have been developed to assist Investigators with select toxicities and can be found in **Appendix B.** Toxicities for which management algorithms have been developed include:

- Pulmonary
- Gastrointestinal
- Hepatic
- Endocrine
- Dermatologic
- Neurologic
- Renal
- Myocarditis

Subjects who experience the following must have all study drugs held:

- Select drug-related AEs and drug-related laboratory abnormalities:
 - o Grade ≥ 1 pneumonitis
 - o Increase from baseline of ≥ one grade (to at least grade 2) of AST, ALT, and/or total bilirubin
 - \circ Grade ≥ 2 creatinine
 - \circ Grade \geq diarrhea or colitis
 - o Grade \geq 2 neurological AE
 - o Grade 4 amylase and/or lipase abnormalities regardless of symptoms or clinical manifestations
 - o Troponin >ULN requires a dose delay to allow for prompt cardiac evaluation
 - Between > 1 to $2 \times ULN$ will be permitted if a repeat assessment remains $\leq 2 \times ULN$ and patient undergoes a cardiac evaluation
- Any AE, laboratory abnormality, or intercurrent illness which, in the judgment of the investigator, warrants delaying the dose of study drug.

Subjects not meeting guidelines for permanent discontinuation will be permitted to resume therapy when the treatment-related AE(s) resolve to grade ≤ 1 or baseline value, with the following exceptions:

- If the toxicity resolves to ≤ Grade 1 or baseline > 6 weeks after last dose, but the subject does not otherwise meet criteria for permanent discontinuation, and the Investigator believes that the subject is deriving clinical benefit, then the subject may be eligible to resume the study drugs following the approval of the IND Sponsor.
- Subjects with grade 4 drug-related amylase and/or lipase increase that is not associated with symptoms or clinical manifestations of pancreatitis can be restarted on therapy once the levels have recovered to grade 3 or less.
- Subjects may resume treatment in the presence of Grade 2 fatigue.

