6.1.1 Adverse Event

An AE is defined as any undesirable sign, symptom or medical condition occurring after starting the study drug (or therapy) even if the event is not considered to be related to the study. An undesirable medical condition can be symptoms (e.g., nausea, chest pain), signs (e.g., tachycardia, enlarged liver) or the abnormal results of an investigation (e.g., laboratory findings, electrocardiogram). Medical conditions/diseases present before starting the study treatment are only considered AEs if they worsen after starting the study treatment (any procedures specified in the protocol). New medical conditions / diseases occurring before starting the study treatment but after signing the informed consent form will not be recorded as AEs. Additionally, expected progression of the disease being studied will not be recorded as an adverse event.

Laboratory abnormalities: Laboratory abnormalities present at the screening visit will be recorded as pre-treatment signs and symptoms. After study treatment administration, all grade 3 and 4 clinical laboratory results that represent an increase in severity from baseline will be reported as AEs. A grade 1 or 2 clinical laboratory abnormality should be reported as an AE only if it is considered clinically significant by the investigator (induce clinical signs or symptoms or require corrective therapy), meets the definition of an SAE, or requires the participant to have study drug discontinued or interrupted. It is expected that

wherever possible, the clinical rather than laboratory term would be used by the reporting investigator (e.g., anemia versus low hemoglobin value).

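### The treatment-emergent laboratory summary counts only normal-to-abnormal changes, so low-grade worsening from an abnormal baseline is counted nowhere

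*Combined protocol and SAP*

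**What the plan says.** Section 12.2 of the combined protocol and SAP plans two summaries of laboratory values:

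- Change over time: "Changes in vital signs, hematology and clinical chemistry parameters from baseline to the end of the study will be examined".
- Shift: "Treatment-emergent changes from normal to abnormal values in key laboratory parameters will be identified". The parameters that count as key are not listed, and no denominator is given.

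The same section plans graded toxicity reporting: "Toxicity will be tabulated by type and grade", using CTCAE v5.0. When an adverse event recurs in a patient, "the highest grade and strongest relationship to study drug will be assumed".

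Three other sections bear on the point.

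- Section 3.1.12 sets organ-function limits that allow abnormal values at entry. For lipase and amylase above the stated limit it adds that subjects with values above 1.5 "ULN may enroll if there are neither clinical nor radiographic signs of a pancreatitis".
- Section 6.1.1 defines which laboratory results become adverse events. After treatment starts, "all grade 3 and 4 clinical laboratory results that represent an increase in severity from baseline will be reported as AEs". For lower grades, "A grade 1 or 2 clinical laboratory abnormality should be reported as an AE only if it is considered clinically significant by the investigator", or if it meets the SAE definition or causes study drug to be stopped or interrupted.
- Section 5.2 lists drug-related findings that require study drug to be held, among them "Increase from baseline of ≥ one grade (to at least grade 2) of AST, ALT, and/or total bilirubin".

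Section 10.2 lists hematology, serum chemistry, thyroid tests and troponin as safety measures, separately from drug-related toxicity by grade.

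**The concern.** A normal-to-abnormal rule needs a normal starting value. A patient who enters with raised ALT, low hemoglobin or raised lipase has already left the normal range, so no later value in that parameter can qualify, whether it doubles or rises tenfold. The protocol expects such patients: section 3.1.12 admits them, and section 5.2 has a resumption rule for patients with grade 1 AST, ALT or bilirubin at baseline.

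Elsewhere the protocol judges laboratory worsening against the patient's own baseline, in section 5.2 for the hepatic hold and in section 6.1.1 for adverse event reporting. The shift summary in section 12.2 does not.

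Safety is the only secondary objective, and laboratory measures are named components of it. A reader of the shift summary could take it as the full account of laboratory worsening, when it leaves out the patients with least reserve in the parameter concerned.

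**Working it through.** The plan states no figure on this point, so there is none to reproduce. The check sets the rules side by side and follows each type of patient through them.

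**Baselines that can be abnormal (section 3.1.12).** AST and ALT up to 3.0 × ULN; total bilirubin up to 1.5 × ULN; creatinine up to 1.5 × ULN, or above that with a clearance of at least 40 mL/min; hemoglobin from 8.5 g/dL; lipase or amylase above 1.5 × ULN without signs of pancreatitis.

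**Routes into a table.** (i) The shift summary in 12.2, which needs a normal baseline. (ii) The adverse event and graded toxicity tables in 12.2, fed by 6.1.1, which needs grade 3–4 worsening from baseline, or a grade 1–2 finding that is clinically significant, is an SAE, or leads to interruption or discontinuation. (iii) The change-from-baseline summary in 12.2, which includes every baseline but names no statistic and no worst value.

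| Case | Shift summary | Adverse event and graded tables |
|---|---|---|
| Normal baseline, brief abnormal value | Counted; the rule is not tied to the last visit | Only if 6.1.1 is met |
| Abnormal baseline, worsens to grade 3–4 | Not counted | Counted, however brief |
| Abnormal baseline, drug-related AST, ALT or bilirubin rises at least one grade to grade 2, or creatinine rises to grade 2 | Not counted | Counted; 5.2 requires a hold, and under 6.1.1 a hold makes it an adverse event |
| Abnormal baseline, worsens within grade 1–2, not clinically significant, not an SAE, no interruption or discontinuation | Not counted | Not counted |

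Only the last row is missing from both counts. It can occur in practice. The listed hold in 5.2 for lipase and amylase starts at grade 4, and hemoglobin and albumin have no listed hold, so low-grade worsening in these reaches the adverse event data only through the investigator's judgement or an SAE. The hepatic and creatinine holds are listed under drug-related findings, so a grade 2 rise put down to another cause need not trigger one.

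The two middle rows are a smaller matter. The events are reported, but the laboratory summary omits worsening that the adverse event tables show for the same patients.

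**The change-from-baseline summary.** Section 12.2 does not say whether the comparison to the end of the study uses the last value or all values over the period. If only the last value is used, worsening that has recovered does not show. If all values are used, it contributes to the summary, but still not as a count of patients who worsened. The sentence names vital signs, hematology and chemistry. For thyroid tests and troponin, the shift summary is therefore the only value-based summary in 12.2, and only if they count as key.

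**Which values are available.** The calendars in 9.1 and 9.2 schedule hematology and chemistry at screening, in each cycle, at EOT and in clinical follow-up. None is scheduled at the safety follow-up, which section 4.12.1 describes as a telephone or email contact at 100 days. Patients who have progressed go to survival follow-up (4.12.3), where no laboratory tests are scheduled.

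**The case against.** The strongest reply is that section 12.2 should be read whole. It plans a graded toxicity table with the highest grade kept, and section 6.1.1 feeds that table relative to baseline. Anything clinically important is therefore reported whatever the baseline: all grade 3–4 worsening, lower-grade worsening that the investigator finds significant, and worsening that stops treatment. A shift summary and an adverse event table also answer different questions, so a difference between them is not a contradiction. All of this stands, and it limits the point to the last row of the table above.

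Three stronger readings are tempting, and the documents do not support them.

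- A reader might infer that a large transient liver-test peak from a raised baseline would vanish. It would not. A grade 3–4 result worse than baseline is an adverse event under 6.1.1. Section 4.10.2 also lists treatment-related ALT or AST above 8 × ULN, of any duration, as requiring discontinuation.
- A reader might infer that transient peaks drop out in general. For a patient normal at baseline, any abnormal value after treatment starts qualifies as a shift. Loss of peaks from the change summary is one reading of an unclear sentence, not a stated rule.
- A reader might try to turn the omission into a percentage by which the event rate is understated. Section 12.2 says that the changes will be identified. It defines no rate and does not say whether patients abnormal at baseline would be in a denominator. The documents also do not give the share of such patients.

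The reply does not cover the remaining gap. The adverse event route for grade 1–2 findings depends on judgement, SAE status or a treatment interruption. A value-based table is the check that does not depend on these, and as written it excludes every patient with an abnormal baseline in the parameter.

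**Conclusion.** The point holds in a narrow form. The treatment-emergent laboratory summary in 12.2 cannot count a patient in a parameter that was abnormal at baseline. For grade 3–4 worsening and grade 2 worsening that triggers a hold, the consequence is only that the laboratory summary omits what the adverse event tables show. For grade 1–2 worsening that is not judged significant, is not an SAE and leads to no interruption or discontinuation, no planned table counts it. The list of key parameters and the time points of the change summary are also undefined.

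No size can be attached, for the reasons given above. The conclusion rests on two readings: that normal-to-abnormal means what it says, and that 6.1.1 is applied as written. It does not affect the primary endpoint or the halting rule in section 4.7, which uses unacceptable toxicity and not laboratory shifts. This is a minor improvement to descriptive safety reporting in cohorts of up to 32 evaluable patients. It is worth making because the data are already collected.

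**What to change.** In section 12.2:

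1. Replace the normal-to-abnormal sentence with a CTCAE v5.0 table of baseline grade against worst post-baseline grade, for each laboratory parameter and each cohort.
2. Count an increase of at least one grade as treatment-emergent, whatever the baseline grade.
3. Use all laboratory values collected on treatment and through EOT, plus any later values that happen to be collected up to 100 days after the last dose. Do not imply complete laboratory coverage to day 100, since no tests are scheduled at that contact.
4. List the parameters in the table in place of the undefined reference to key ones, and say whether thyroid tests and troponin are among them.
5. State that the change-from-baseline summary gives the worst on-treatment value as well as the last value.

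The cost is analysis wording and table programming. No new visits, samples or data fields are needed, and the adverse event rules in 6.1.1 and the hold rules in 5.2 stay as they are.
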